#### 6.2.4 Analysis of the primary efficacy variable

The primary analysis will include events as adjudicated by the ICAC and will be based on the ITT analysis set using the ITT data scope.

In order to evaluate whether rivaroxaban is superior to ASA in prolonging the time to a primary efficacy (PE) outcome event in patients with ESUS, the following null hypothesis ( $H_0$ ) will be tested at the significance level of 0.025:

$H_{0, PE}$ :  $S_R(t) = S_A(t)$  for all time points  $t \geq 0$ , (i.e. “there is no difference between the rivaroxaban treatment group and the ASA control group regarding the primary efficacy outcome for all time points”)

The one-sided alternative hypothesis will be:

$H_{1, PE}$ :  $S_R(t) > S_A(t)$  for at least one time point  $t \geq 0$ , and  $S_R(t) \geq S_A(t)$  for all time points  $t \geq 0$ , (i.e. “there is a difference between the two groups in favor of rivaroxaban regarding the primary efficacy outcome for at least one time point”)

where  $S_R$  denotes the survival function of the rivaroxaban and  $S_A$  denotes the survival function of the ASA group.

The following decision rule to test the null hypothesis will be applied:

According to the size of this study, it is justified to assume under  $H_{0, PE}$  a sufficiently close approximation of the one-sided stratified (according to dichotomic age group) log-rank test to the normal distribution. If the z-value from the one-sided log-rank test (for the difference  $S_R(t) - S_A(t)$  with stratification) is larger than the critical quantile from the normal distribution ( $z_{0.975} = 1.96$ ), the null hypothesis will be rejected in favor of the alternative hypothesis.

Kaplan-Meier estimates of cumulative risk and Nelson-Aalen estimates of the cumulative hazard functions will be provided to evaluate the timing of event occurrence in the different treatment groups and the consistency of the respective treatment effects for all time points.

To derive the log-rank Z test statistic and the variance V of the log-rank statistics, SAS program code corresponding to the following will be used:

```

PROC LIFETEST DATA = <dataset> ALPHA=0.05 METHOD=KM NELSON;
  STRATA stratumn / GROUP=trtgrpn TEST=(LOGRANK);
  TIME ttevalue * ttecnsr(0);
RUN;

/*
where
dataset = name of sub-dataset including all ITT subjects randomized
trtgrpn = variable coding randomized treatment group
ttevalue = time to first occurrence of primary efficacy outcome event
ttecnsr = censoring index (0 = right-censored, 1 = event)
stratumn = variable for stratification factor (age group with two levels)
*/

```

Hazard ratio and corresponding two-sided 95% confidence intervals will be estimated based on an age-group stratified Cox proportional hazards models. The plausibility of proportional hazards assumption will be assessed by visually comparing the plot of the log of cumulative hazard between treatments and by additionally adding a treatment by logarithm-transformed time interaction into the Cox model. Censoring will be assumed independent of the treatment group assignment.

For the analysis of the primary outcome in this study, the hazard function  $h(t)$  is the chance that an individual experiences an event of the primary efficacy outcome in the next instant in time, given that the individual has not had such an event up to time  $t$ . For example, for the comparison of rivaroxaban with ASA (control), the corresponding stratified Cox proportional hazards model can be described by the following equation:

$$h_k(t, x_i) = h_{0k}(t) \exp(\beta x_i),$$

where

$h_k(\cdot)$  hazard function for primary efficacy outcome for stratum  $k$ ,  $k = 1, 2$   
( $k$  represents age group stratification factor), as a function of time and subject's covariates

$h_{0k}(\cdot)$  unspecified underlying baseline hazard function for primary efficacy outcome per stratum  $k$ ; hazard of an individual with  $x_i = 0$

$t$  time (in days) relative to the randomization date

$x_i$  treatment group of subject  $i$

$\beta$  unknown parameter (to be estimated); hazard ratio =  $\exp(\beta)$

SAS program code corresponding to the following will be used:

```
PROC PHREG DATA = <dataset>;
  MODEL ttevalue * ttecnsr(0) = trtgrp / RL TIES=EFRON ALPHA=0.05;
  STRATA stratumn;
RUN;

/*
where
dataset = name of sub-dataset including all ITT subjects
trtgrp   = variable coding randomized treatment group
ttevalue = time to first occurrence of primary efficacy outcome event
ttecnsr  = censoring index (0 = right-censored, 1 = event)
stratumn = variable for stratification factor (age group with two levels)
*/
```

Additional procedure options controlling the output may be added to the program codes.

Subjects without a primary efficacy outcome event will constitute a right-censored observation (see section 4.5.3 for censoring rules). Primarily, for the time-to-event analysis the censoring mechanism will be assumed to be non-informative. Additional sensitivity analyses will be performed in order to evaluate the robustness of the statistical results under different assumptions (see section 6.2.7).

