Number of subjects	
The study is event-driven and it is estimated that approximately 7000 patients (3500 per treatment group) are to be enrolled in order to have 450 patients experiencing a positively adjudicated primary efficacy outcome event.
 
The number of patients enrolled in the total study may be adjusted or enrollment in the age group 50-59 years may be stopped based on a blinded review of the observed overall event rate of confirmed primary efficacy outcomes during the study.⁵

Primary variable	
Time from randomization to first occurrence of any of the components of the composite outcome (adjudicated); including:
 
 • Stroke (ischemic, hemorrhagic, and undefined stroke, transient ischemic attack with positive neuroimaging) • Systemic embolism
Plan for statistical analysis	
The primary efficacy analyses will be based on the intent-to-treat population. Rivaroxaban treatment will be compared with the aspirin control group using a stratified log-rank test. Kaplan-Meier curves for the cumulative incidence risk and cumulative incidence functions will be provided to evaluate the timing of event occurrence. Risk reduction will be estimated with the stratified Cox proportional hazards model.
 
Secondary efficacy outcomes will be analyzed using similar methods as for the primary efficacy analysis. Testing will be performed in hierarchical order.
 
There will be 2 formal interim analyses to assess efficacy and stop for overwhelming superiority, which will occur when approximately 50% and 67% of the planned primary efficacy outcomes have accrued.⁶
 
The analysis of the safety outcomes will be similar to those described for the primary efficacy outcome.

Anticipated total study duration and study duration per patient	
Total study duration: ~3 years Randomization period: ~2 years Treatment duration of last patient randomized: ~1 year Mean treatment duration per patient: ~2 years
 
The study is event driven and these timelines may vary depending on the enrollment rate and event rate in the study.

⁵ Sentence was revised with global Protocol Amendment 5. See Section 13.1 for details.

⁶ A second interim analysis was added with global Protocol Amendment 5. See Section 13.1 for details.

Table of procedures – amended ⁷

	Screen	Random	Treatment Phase						Washout
	V1	V2	V3	V4	V5	V6	V7-V [∞]	EOT ^a	Safety Visit

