8.4.1 Analysis of the primary efficacy variable

In order to evaluate whether rivaroxaban is superior to ASA in prolonging the time to a primary efficacy outcome event in patients with ESUS, the following null hypothesis (H) will be tested at the significance level of 0.025:

$H_{0, PE}: S_R(t) = S_A(t)$ for all time points $t \geq 0$, (i.e. “there is no difference between the rivaroxaban treatment group and the ASA control group regarding the primary efficacy outcome for all time points”)

The one-sided alternative hypothesis will be:

$H_{1, PE}: S_R(t) > S_A(t)$ for at least one time point $t \geq 0$, and $S_R(t) \geq S_A(t)$ for all time points $t \geq 0$, (i.e. “there is a difference between the two groups in favor of rivaroxaban regarding the primary efficacy outcome for at least one time point”)

where S_R denotes the survival function of the rivaroxaban and S_A denotes the survival function of the ASA group.

The following decision rule to test the null hypothesis will be applied:

According to the size of this study, it is justified to assume under $H_{0, PE}$ a sufficiently close approximation of the one-sided stratified (according to age) log-rank test to the normal distribution. If the z-value from the one-sided log-rank test (for the difference

$S_R(t) - S_A(t)$ with stratification⁴²) is larger than the critical quantile from the normal distribution ($z_{0.975} = 1.96$), the null hypothesis will be rejected in favor of the alternative hypothesis.

Kaplan-Meier estimates of cumulative risk and cumulative hazard functions will be provided to evaluate the timing of event occurrence in the different treatment groups and the consistency of the respective treatment effects for all time points.

Hazard ratio, relative risk reduction, and corresponding two-sided 95% confidence intervals will be estimated based on an age-group stratified Cox proportional hazards models. The plausibility of proportional hazards assumption will be assessed by visually comparing the plot of the log of cumulative hazard between treatments and by additionally adding a treatment by logarithm-transformed time interaction into the Cox model. Censoring will be assumed independent of the treatment group assignment.

Further details will be specified in SAP.

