## 4.5 Data Rules

### 4.5.1 Analysis Dates - amended

For the study the following date and time window are of relevance for the analysis:

- Efficacy cut-off date:  
The efficacy cut-off date is the 5th of October 2017, the date the early stopping of the trial was officially announced.
- Trial close-out window:  
The Trial close-out window is the time period when all subjects are to return to the clinic for an End of treatment Visit.

For each subject, the following individual dates are of relevance for analysis:

- Randomization date:  
The date of randomization to antithrombotic study treatment of the subject.
- End of treatment (EOT) Visit date:  
This is the date of the EOT Visit for the individual subject.  
After the announcement of the end of the study, all subjects are to return to the clinic for their EOT Visit within the pre-specified window (Trial close-out window).  
If subjects do not have an EOT visit, the date will be missing.
- Date of the last contact prior or equal to efficacy cut-off:  
This date is defined as the date of the last trial contact or the efficacy cut-off date, whatever comes first.
- Date of the last trial contact:  
The date of the last documented contact with the subject or a third party (including data on subject survival status).  
For subjects who die after randomization the date of the last contact is set to the death date.
- Date of first double-blind dose of antithrombotic study treatment:  
The date of the first dose of rivaroxaban / aspirin study medication.
- Date of last double-blind dose of antithrombotic study treatment:  
The date of the last dose of rivaroxaban / aspirin study medication.  
For a subject with permanent discontinuation of any study medication, the corresponding last dose date(s) will be obtained from the CRF "Study Medication Discontinuation/Restart Report". If study medication was continued until the EOT visit, the date of the last dose of the corresponding study medication will be as reported on the EOT visit CRF.  
If missing or incomplete, the date of last double-blind dose of antithrombotic study

treatment is set to the latest logically possible date of antithrombotic study medication administration on or before the earliest of the subject's following dates, the date of last trial contact, the date of death, or the efficacy cut-off date, and no earlier than the randomization date.

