##### **Censoring rules for analyses according to the intention-to-treat principle**

For analyses according to the intention-to-treat principle, randomized subjects without documentation of an event will be censored at the efficacy cut-off date or the date of the last trial contact, whatever comes first.

This censoring rule will be applied to all analyses according to the intention-to-treat principle. In the rare event that for a subject only survival status information can be retrieved at the end

of the study but no information on other outcomes, the last follow-up / trial contact where survival status information was obtained will still be used to determine the censoring date for the subject and if there were no known events up to then the subject will be considered as event-free.

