## 6.6 Net clinical Benefit

The benefit-risk of rivaroxaban vs aspirin will be evaluated based on the excess number of events between treatments for events intended to be prevented (benefits) and events that may be caused (risks). Excess number of events is defined as the difference in event rate times a hypothetical population size (eg, 10,000 patients). To have a comprehensive benefit-risk evaluation, several comparisons will be considered.

The first measure of net clinical benefit in this study is the primary efficacy outcome. Although named efficacy outcome it includes not only thrombotic events, but also hemorrhagic events (hemorrhagic stroke).

The second measure of net clinical benefit is all-cause mortality.

The third measure of net clinical benefit is the composite of stroke, MI, CV death, fatal bleeding or bleeding into a critical organ.

As an overall valid measure of net clinical benefit is hard to be defined, a variety of measures will be presented side by side to allow weighting positive effects and harms. For the efficacy these will include the thrombotic events of the primary and secondary efficacy endpoints. For the safety side these will include the hemorrhagic events of the efficacy endpoint, ISTH major bleeding, life-threatening bleeding, and intracranial hemorrhage.

Other measures may be added as they may help to assess the net clinical benefit.

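### Kaplan-Meier cumulative risk with other deaths censored slightly overstates absolute risk, and the protocol synopsis, protocol 8.4.1 and SAP 6.2.4 do not name the same estimators

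*SAP*

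**What the plan says.** Three places describe the curves for the primary outcome, and they differ.

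- Protocol synopsis, plan for statistical analysis: "Kaplan-Meier curves for the cumulative incidence risk and cumulative incidence functions will be provided to evaluate the timing of event occurrence".
- Protocol 8.4.1: "Kaplan-Meier estimates of cumulative risk and cumulative hazard functions will be provided".
- SAP 6.2.4: "Kaplan-Meier estimates of cumulative risk and Nelson-Aalen estimates of the cumulative hazard functions will be provided".

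The treatment of deaths follows from three SAP rules.

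- SAP 4.5.1: "For subjects who die after randomization the date of the last contact is set to the death date".
- SAP 4.5.3, intention-to-treat rules: "randomized subjects without documentation of an event will be censored at the efficacy cut-off date or the date of the last trial contact", whichever is earlier.
- SAP 6.2.4: "Subjects without a primary efficacy outcome event will constitute a right-censored observation". The program code there uses a two-level index (censored or event), with no code for a competing event.

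Fatal strokes count as events (protocol 7.3.2.1), so only deaths without a prior primary event are censored. SAP 6.2.5 and 6.4.5 carry the same methods over to the secondary efficacy and bleeding outcomes. No competing-risk method appears in SAP 6.2.4, 6.2.5, 6.2.7 or 6.4.5, and the change log in SAP section 7 does not record that one was dropped.

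**The concern.** A patient who has died cannot later have a stroke. Censoring that patient at death lets Kaplan-Meier act as if the stroke could still happen at the rate seen in survivors. The complement of the curve is then a risk in a hypothetical population with no other deaths, yet SAP 6.2.4 labels it cumulative risk without qualification. The plan assumes 3% deaths per year against 3.8% primary events per year, so the competing event cannot be dismissed without a check.

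Absolute risks and risk differences by arm are at stake. They matter here because the SAP introduction reports that the trial stopped on a bleeding excess without offsetting benefit, so readers will weigh absolute numbers. Separately, someone who reads only the synopsis would expect cumulative incidence functions that the SAP does not specify.

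**Working it through.** **Inputs** (SAP 4.6, same values in protocol 8.6): aspirin event rate 3.8% per year; deaths 3% per year; expected observed relative risk reduction 26%, so HR = 0.74; 450 events; one-sided alpha 0.025; 1:1 allocation; 2 years' recruitment and 3 years' total duration.

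**The plan's own figures.** Event rate: 0.9 × 4.0% + 0.1 × 2.0% = 3.8%. Power by Schoenfeld's formula: √450 / 2 × |ln 0.74| − 1.96 = 10.607 × 0.3011 − 1.96 = 1.234, which gives 89.1% against the stated 90%. In reverse, HR 0.74 at 90% power needs 464 events; an HR of 0.736 to 0.737 needs 448 to 452, so rounding of the 26% explains the gap. The design reproduces, and none of this depends on the estimator of absolute risk.

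**Size of the overstatement.** Assume constant cause-specific hazards: l for the primary event, d for death without a prior primary event.

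- Kaplan-Meier target with deaths censored: 1 − exp(−lT)
- Cumulative incidence (Aalen-Johansen target): l/(l+d) × [1 − exp(−(l+d)T)]

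Take l = 0.038 (aspirin), l = 0.038 × 0.74 = 0.02812 (rivaroxaban) and d = 0.03. For aspirin at 2 years, Kaplan-Meier gives 1 − exp(−0.076) = 7.32%, and cumulative incidence gives 0.038/0.068 × [1 − exp(−0.136)] = 7.11%.

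| | Kaplan-Meier | Cumulative incidence | Excess |
|---|---|---|---|
| Aspirin, 1 year | 3.73% | 3.67% | 0.06 points |
| Aspirin, 2 years | 7.32% | 7.11% | 0.21 points (3.0% relative) |
| Aspirin, 3 years | 10.77% | 10.31% | 0.46 points (4.5% relative) |
| Rivaroxaban, 2 years | 5.47% | 5.31% | 0.16 points |
| Rivaroxaban, 3 years | 8.09% | 7.74% | 0.35 points |
| Difference, 2 years | 1.85 points | 1.80 points | about 0.05 points |
| Difference, 3 years | 2.68 points | 2.57 points | about 0.11 points |

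**Sensitivity.**

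- Reading the yearly figures as annual risks, with hazard = −ln(1 − risk), gives 10.97% against 10.50% for aspirin at 3 years. The difference between arms is then 273 against 261 per 10,000. The message is the same.
- Varying d from 1% to 5% per year (an assumption) gives a 3-year aspirin excess of 0.16 to 0.75 points, or 1.5% to 7.5% relative. At d = 2% the 2-year excess is 0.14 points (7.32% against 7.18%).
- The relative excess hardly depends on the event rate. With d = 0.03, event rates of 4% and 2% per year both give about 3.0% at 2 years and 4.5% at 3 years. The documents give no bleeding rates, so no absolute figure is computed for bleeding.

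**The case against.** The case on the other side is substantial, and much of it stands.

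- *SAP 6.6 need not be affected.* A reader might infer that the excess-event counts are biased upwards. The text does not support that: "Excess number of events is defined as the difference in event rate times a hypothetical population size", and it does not say whether the rate is a Kaplan-Meier risk, a crude proportion or a person-time rate. Kaplan-Meier bias enters only in the first case. This stands.
- *The 3-year figures are a high estimate.* The synopsis gives a mean treatment duration of about 2 years, and the SAP fixes the cut-off at 5 October 2017, before the planned end in 2018. The 3% is stated for all deaths, so it covers fatal strokes and deaths after a non-fatal event, which do not compete. This stands, and it is why the 2-year figures lead.
- *The bias is small against sampling error.* With 3500 per arm and no censoring, the standard error of the 2-year difference is √[(0.0711 × 0.9289 + 0.0531 × 0.9469)/3500], about 0.58 points, against a bias of 0.05. The inflation of the difference also assumes HR 0.74; with an HR near 1 and similar mortality it would be close to zero. Both stand.
- *The synopsis wording may be a slip.* It uses cumulative incidence for the Kaplan-Meier curve itself, and the parallel sentence in 8.4.1 has cumulative hazard. A reader might infer that a promised analysis was dropped; the documents do not show that. The mismatch still needs correcting.
- *Breadth.* All-cause mortality has no competing death. The first secondary composite already counts cardiovascular deaths and those of undetermined cause (SAP 6.2.2), so only non-cardiovascular deaths compete there. This stands and limits the fix.
- *Output layouts are in a separate document* (SAP section 1) that was not available. That does not excuse the SAP from naming its estimator.

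**Conclusion.** The point holds as a minor matter of reporting and consistency. SAP 6.2.4 calls a Kaplan-Meier quantity cumulative risk when deaths outside the outcome are censored, and this overstates absolute risk. On the plan's rates the aspirin-arm excess is at most about 0.2 points at 2 years and 0.5 points at 3 years. The between-arm difference at HR 0.74 is inflated by about 0.05 and 0.11 points. These figures rest on constant hazards and on treating all 3% yearly deaths as competing, so they lie near the upper end for these inputs.

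A reader might also infer that the primary result is compromised. It is not. With competing deaths censored, the log-rank test and Cox model compare cause-specific hazards, which is a valid comparison, and power depends on the 450 events.

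The synopsis, protocol 8.4.1 and the SAP need to be aligned whatever the size of the bias.

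**What to change.** 1. In SAP 6.2.4, and by reference in 6.2.5 and 6.4.5, add Aalen-Johansen cumulative incidence estimates by arm, with death not part of the outcome as a competing event. Apply them to the primary outcome, the secondary outcomes other than all-cause mortality, and the bleeding outcomes. This needs a third level in the event index. State for each outcome which deaths compete: for the primary outcome, any death without a prior primary event; for the first secondary composite, non-cardiovascular deaths only.
2. Use these estimates for reported absolute risks and for any cumulative risk used in SAP 6.6, and state in 6.6 which kind of rate is meant.
3. Align the synopsis, protocol 8.4.1 and SAP 6.2.4, and record the change in SAP section 7. If the synopsis meant cumulative hazard, say so there.
4. Leave the stratified log-rank test, the Cox model and the significance level unchanged. The Kaplan-Meier and Nelson-Aalen plots can stay for judging the timing of events.

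Cost: one more output per outcome, and slightly lower reported absolute risks.

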### 6.2.5 Analysis of secondary efficacy variables

A single primary efficacy outcome will maintain strict control of the type I error rate. If the primary efficacy outcome is statistically significant, the secondary efficacy outcomes will be tested in a sequential manner according to the order as listed in section 6.2.2.

If the superiority of rivaroxaban for the primary outcome is declared, the following alternative hypotheses, superiority of rivaroxaban compared with ASA for the secondary efficacy outcomes will be tested in the sequential order. That is, the subsequent ordered secondary outcome will be tested only if superiority can be shown for the previous outcomes.

If an individual test during any step is not statistically significant, further testing may continue but significance will not be claimed. This hierarchical testing procedure will control the global Type 1 error level.

The primary analysis of the secondary variables will include events as adjudicated by the ICAC and will be based on the ITT analysis set using the ITT data scope.

The first secondary efficacy variable (SE1) of this study is the time from randomization to first occurrence of cardiovascular death (including death due to hemorrhage), recurrent stroke, systemic embolism, or MI. The following null hypothesis will be tested at the significance level of 0.025:

$H_{0, SE1}: S_{R1}(t) = S_{A1}(t)$  for all time points  $t \geq 0$ ,

The one-sided alternative hypothesis will be:

$H_{1, SE1}: S_{R1}(t) > S_{A1}(t)$  for at least one time point  $t \geq 0$ , and  $S_{R1}(t) \geq S_{A1}(t)$  for all time points  $t \geq 0$ ,

where  $S_{R1}$  denotes the survival function of the rivaroxaban and  $S_{A1}$  denotes the survival function of the ASA group.

The second secondary efficacy variable (SE2) of this study is the time from randomization to first occurrence of death from any cause. The following null hypothesis will be tested at the significance level of 0.025:

$H_{0, SE2}: S_{R2}(t) = S_{A2}(t)$  for all time points  $t \geq 0$ ,

The one-sided alternative hypothesis will be:

$H_{1, SE2}: S_{R2}(t) > S_{A2}(t)$  for at least one time point  $t \geq 0$ , and  $S_{R2}(t) \geq S_{A2}(t)$  for all time points  $t \geq 0$ ,

where  $S_{R2}$  denotes the survival function of the rivaroxaban and  $S_{A2}$  denotes the survival function of the ASA group.

The analysis methods will be those described for the primary efficacy outcome.

The same analysis will be performed for the individual components of the primary and secondary efficacy outcomes (stroke, CV death, and MI) as well as ischemic stroke, and disabling stroke (modified Rankin score 4 and 5).

